Pre-existing conditions (i.e., undesirable experiences, signs or symptoms that begin prior to the Screening Visit) will be recorded on the medical history eCRF pages. During the study, site personnel will record any change in the condition(s) and occurrence and nature of any AEs. Signs and symptoms that are believed to be due to the pre-existing condition(s) (started prior to dose of study medication) do not have to be recorded in the AEs section of the eCRF, unless there is an increasing in frequency and severity. Additionally, signs or symptoms or changes in pre-existing conditions that occur outside the trial defined adverse event reporting period (e.g., between each imaging visit will be recorded in medical history).

An adverse event is any untoward medical occurrence associated with the use of a drug in humans, whether or not considered drug related. For the purposes of this study, untoward medical occurrences will be considered associated with the use of ¹⁸F-AV-1451, and thus be reported as adverse events, if they occur within 48 hours after administration of ¹⁸F-AV-1451. Untoward medical occurrences will be considered associated with the use of Florbetapir F 18 injection, if they occur within 48 hours after Florbetapir F 18 injection administration. Adverse events associated with the use of ¹⁸F-AV-1451 or Florbetapir F 18 injection will be recorded as treatment emergent relative to the respective drug. Adverse experiences that occur after administration of either drug but outside the 48 hour reporting window will not be reported unless the investigator believes they are attributable to the drug.

Trial-emergent adverse events are undesirable experiences, signs or symptoms that begin, or worsen in intensity or frequency, after the informed consent, and

Protocol ¹⁸F-AV-1451-A19: “¹⁸F-AV-1451 PET Imaging in Subjects with Frontotemporal Dementia”

prior to administration of study drug at the imaging visit. In order to capture possible adverse effects of trial participation, trial-emergent AEs will also be reported during the baseline imaging period but not during the 48 hour windows following the administration of ¹⁸F-AV-1451 or Florbetapir. These will be recorded on the adverse event pages.

The end of study, for the purpose of adverse event reporting, is defined as 48 hours after the last study drug administration.

Serious Adverse Event (SAE)

A SAE is an AE that results in one of the following outcomes or constitutes one of the following events:

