7.7.4. Reporting of Serious Adverse Events

Study site personnel must alert Eli Lilly, or its designee, of any SAE within 24 hours of their awareness of the event via a sponsor-approved method. Alerts issued via telephone are to be immediately followed with official notification on study-specific SAE forms.

Serious adverse events occurring after a subject receives a dose of study drug will be collected in the eCRF as Adverse Events until 48 hours after the dosing of the study drug, regardless of the investigator's opinion of causation. Thereafter, SAEs are not required to be reported in the eCRF as Adverse

Events unless the investigator feels the events were related to either investigational product or drug delivery system, or a protocol procedure. If the investigator does not feel the event was related to the investigational product or drug delivery system or protocol procedure, then the event should be recorded in the eCRF as Medical History for the subject. Regardless of the investigator’s assessment of relatedness or timing, all SAEs that occur after the subject receives the investigational product should be submitted to Lilly GPS for processing to determine applicability of any expedited reporting requirements..

If a patient experiences a SAE after signing informed consent, but prior to receiving study drug, the event will NOT be reported unless the investigator feels the event may have been caused by a protocol procedure. Previously planned (prior to signing the ICF) surgeries should not be reported as SAEs unless the underlying medical condition has worsened during the course of the study.

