6.6.2 Adverse Events

All adverse events (AEs) occurring after signing the informed consent are to be recorded on the AE pages of the case report form (CRF). Any pre-existing conditions (i.e., undesirable experiences, signs or symptoms that begin prior to the Screening Visit) will be recorded on the medical history eCRF pages. The investigator's verbatim term of AEs will be mapped to SOC and PT using the MedDRA v 21.1 or higher.

Adverse Events:

An AE is any undesirable experience occurring to a subject during a clinical trial, whether or not considered related to the study drug. In this study clinically relevant abnormal finding, as well as worsening of any pre-existing condition shall be recorded as an AE. AEs that occur after administration of either drug but outside 48 hour reporting window will not be reported unless those are attributed to the study drug.

Unexpected Adverse Events:

An unexpected adverse event is an adverse event not previously reported or an adverse event that occurs with specificity, severity or frequency that is not consistent with the current Investigator's Brochure (IB).

Serious Adverse Events (SAEs):

Serious AEs (SAEs) are events that result in one of the following outcomes or constitute one of the following events:

- Death
- Initial or prolonged hospitalization
- A life-threatening experience (that is, immediate risk of dying)
- Persistent or significant disability/incapacity
- Congenital anomaly/birth defect
- Considered significant by the investigator for any other reason

Important medical events that may not result in death, be life-threatening, or require hospitalization may be considered serious adverse drug events when, based upon appropriate medical judgment, they may jeopardize the patient and may require medical or surgical intervention to prevent one of the outcomes listed in this definition.

For the summarization of AEs by seriousness, events recorded with missing seriousness will be summarized as serious, following worst case principle.

Trial Emergent Adverse Events:

Trial Emergent AEs are defined as any AEs that occur or worsen (increase in intensity and/or frequency) after the informed consent, and prior to administration of Florbetapir F 18, or between the Florbetapir F 18 injection session and Flortaucipir F 18 injection session but outside the 48 hours window following administration of Florbetapir F 18 or Flortaucipir F 18.

Treatment Emergent Adverse Events (TEAEs):

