8 STATISTICAL ANALYSIS

8.1 Analysis Populations

The study will use following analysis populations for data summarization. Frequency count and percentage of subjects in each analysis population will be summarized.

Population	Definition	Displays
Enrolled Population	The Enrolled Population will consist of all subjects who signed informed consent and have data captured in the clinical database.	Disposition information will be summarized using the Enrolled Population.
Safety Population	The Safety Population will include all subjects who received at least one dose of Flortaucipir F 18 or Florbetapir F 18 injection.	All demographic, baseline and safety endpoints will be using the Safety Population.
ITT Population	The ITT Population will include all subjects in safety population, for whom image data are available i.e. who have a valid Flortaucipir F 18 scan assessment [SUV _r (quantitative) and/or visual reads (qualitative)].	All analyses involving imaging outcomes will be based on the ITT Population.
Per Protocol Population	The Per Protocol Population will include all subjects in ITT population who were classified on Florbetapir positive ($\alpha\beta+$) by either investigator or Avid.	All analyses involving imaging outcomes will be based on the Per Protocol Population.

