8.10 Analysis of Safety

All safety data will be summarized using the Safety Population.

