8.10.2 Adverse Events

All AE summary tables will include only TEAEs, unless otherwise specified.

Adverse events will be summarized by SOC and PT. A subject will only be counted once per SOC and PT.

For AEs by severity grade (mild, moderate, severe), if a subject has multiple events occurring in the same SOC or same PT, then the event with the maximum intensity (i.e. severe) will be counted.

For AEs by relationship to study drug and protocol procedure will be summarized as Related vs. Not Related. If a subject has multiple events occurring in the same SOC or same PT, the event associated with the study drug will be summarized.

AEs will be summarized by descending frequency, then alphabetically by SOC and preferred term.

An overall summary of AEs will be presented and will include:

- Subjects with any Trial Emergent AEs
- Subjects with at least one TEAE
- Subjects with any severe or moderate TEAE
- Subjects with any TEAE related to Florbetapir F 18
- Subjects with any TEAE related to Flortaucipir F 18
- Subjects with any TEAE related to protocol procedure
- Subjects with any serious TEAE
- Subjects with any TEAE resulting in death
- Subjects with any TEAE leading to study discontinuation

The following summary tables will be presented by SOC and PT:

- Trial Emergent AEs
- All TEAEs
- TEAEs by PT
- TEAEs by severity
- TEAEs by relationship to Florbetapir F 18
- TEAEs by relationship to ¹⁸F-AV-1451
- TEAEs by relationship to protocol procedure
- Serious TEAEs
- TEAEs resulting in death
- TEAEs leading to study discontinuation

The following listings will be presented by subject:

- All AEs
- Serious TEAEs
- TEAEs leading to study discontinuation
- TEAEs resulting in deaths

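### Trial-emergent AEs run from consent but are tabulated only in dosed subjects, so an event in a subject who stops before any injection enters no AE summary table

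*SAP*

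**What the plan says.** **When the trial-emergent period starts.** Protocol 7.7.2: "Trial-emergent adverse events are undesirable experiences, signs or symptoms that begin, or worsen in intensity or frequency, after the informed consent". It introduces the reporting of these events with a purpose: "In order to capture possible adverse effects of trial participation". SAP 6.6.2 starts the period at the same point: "after the informed consent, and prior to administration of Florbetapir F 18". It adds the interval between the two tracer sessions, outside the 48-hour windows.

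**What is collected.** SAP 6.6.2: "All adverse events (AEs) occurring after signing the informed consent are to be recorded on the AE pages".

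**Who is summarized.** SAP 8.1: "The Safety Population will include all subjects who received at least one dose of Flortaucipir F 18 or Florbetapir F 18 injection". SAP 8.10: "All safety data will be summarized using the Safety Population". The Enrolled Population (consented, with data in the database) is assigned to disposition only.

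**What is tabulated.** The overall AE summary in SAP 8.10.2 has a row for "Subjects with any Trial Emergent AEs", and there is a trial-emergent table by SOC and PT. Neither names a population of its own. All other AE tables cover TEAEs.

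**The protocol on safety summaries.** Section 8.1 promises a safety summary for all patients, whereas 8.1.2 bases safety evaluation on the dosed population. Section 8.2.2 promises a summary of every patient with an SAE or an AE leading to discontinuation and does not limit this to events after dosing.

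**The concern.** A dosed-only population is the usual choice for treatment-emergent events, because exposure to the drug starts at the injection. Trial-emergent AEs are a different class. Here the exposure is taking part in the trial, and it starts at consent. Restricting their table to subjects who were later injected means that a subject must complete the pre-injection period before an event in that period can be counted.

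At stake is whether the trial-emergent table is complete. It is the only summary meant to show harms of participation apart from the tracers. With up to 25 subjects planned, its counts are likely to be small, so one missing event could change what a reader takes from it.

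**Working it through.** The plan gives no figure to reproduce. It states no number of consented or never-injected subjects, no screen-failure rate and no AE rate. The check is a trace of one case through every planned display: a subject consents, has an AE during screening, and stops before any injection.

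1. *Class.* The event starts after consent and before any tracer, so it is trial-emergent under Protocol 7.7.2 and SAP 6.6.2. One could argue that the SAP definition ends at an injection that never takes place. In that case the event belongs to neither class, and the result below is the same.
2. *Collection.* SAP 6.6.2 puts it on the AE pages.
3. *Population.* The subject is in the Enrolled Population and not in the Safety Population (SAP 8.1).
4. *Displays.*

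| Display | Content | Population | Case shown? |
|---|---|---|---|
| Overall AE summary, trial-emergent row (SAP 8.10.2) | Trial-emergent AEs | Safety, by SAP 8.10 | No: subject excluded |
| Trial-emergent table by SOC and PT (SAP 8.10.2) | Trial-emergent AEs | Safety, by SAP 8.10 | No: subject excluded |
| All TEAE rows and tables (SAP 8.10.2) | Events from injection to 48 hours | Safety | No: event excluded by definition |
| Listing of all AEs (SAP 8.10.2) | Every AE | None stated | Yes, as written |
| eCRF data listings (SAP 7.1) | Every eCRF item | None stated | Yes, as written |
| Disposition (SAP 8.2) | Discontinuation and reason | Enrolled | Withdrawal yes, AE term not planned |

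The event is counted in none of the AE summary tables and can be seen in the listings.

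5. *Who can be missed.* Only subjects who stop before any injection. Three groups are not missed: subjects excluded for a positive study florbetapir scan (already injected), subjects with a pre-injection event who are dosed later, and subjects with an event between the two tracers after a study florbetapir injection. A subject with an interpretable amyloid scan from the previous 3 years skips florbetapir (Protocol 7.1.1.1) and so stays undosed until the flortaucipir visit. The gap is longest for these subjects.

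6. *Direction of the effect.* Let e_d of n_d dosed subjects and e_u of n_u never-injected subjects have a trial-emergent AE. The plan shows e_d / n_d. All enrolled subjects would give (e_d + e_u) / (n_d + n_u). The planned count is too low by e_u. The planned percentage is too low only if e_u / n_u > e_d / n_d. The documents give none of these four quantities. The planned 25 does not supply n_d + n_u either: the protocol places enrollment after the amyloid read, whereas the SAP's Enrolled Population starts at consent.

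7. *Against the protocol.* Protocol 8.2.2 covers all patients with SAEs or AE discontinuations. SAP 8.10.2 tabulates only serious TEAEs and TEAEs leading to discontinuation, yet SAP 5.2 declares no change from the protocol's analyses. Protocol 7.7.4 says of an SAE after consent and before study drug that "the event will NOT be reported unless the investigator feels the event may have been caused by a protocol procedure". An SAE that the investigator does attribute to a procedure is therefore reportable, but in a never-injected subject it would be in no safety table.

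**The case against.** The strongest case against the point is that nothing is hidden. SAP 8.10 governs what is summarized, not what is listed. Where the SAP restricts a listing to the Safety Population it says so (family history, medical history, medications, pregnancy tests), and the AE listing carries no such restriction. The withdrawal and its reason are tabulated on the Enrolled Population. In a descriptive study of this size, a by-subject listing is a workable display for a rare event. The dosed-only choice also follows Protocol 8.1.2 and suits the secondary objective of expanding the flortaucipir safety database, to which an undosed subject adds no exposure.

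Most of this stands, and it limits the weight of the point. It does not answer it, because the SAP chose to tabulate trial-emergent AEs and, by its own rules, that table omits eligible events.

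Three stronger readings are tempting, and the documents do not support them:

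- *A reader might infer that the event disappears from the report.* The unrestricted listings say otherwise.
- *A reader might infer that procedure-caused events are the ones most likely to end participation, so that the table selectively loses them.* Protocol 7.7.4 shows only that such an SAE is reportable. The procedures before injection are history, MMSE, an ECG unless a recent one exists, an MRI only where no prior scan is available, and a pregnancy blood test for some women. No AE or withdrawal rate is given for any of them.
- *A reader might infer that trial-emergent percentages are biased towards zero by a known amount.* Step 6 shows that only the count has a certain direction, and no size can be derived.

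**Conclusion.** The point holds as a minor gap between a definition and its analysis population. A trial-emergent AE in a consented, never-injected subject is counted in no AE summary table, although the class was set up to capture effects of participation and Protocol 8.2.2 promises a summary of all patients with SAEs or AE discontinuations. The event remains visible in the listings, and the withdrawal in disposition.

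The size is unknown and probably small, given the short list of low-burden procedures before the first injection. The conclusion rests on two readings: that SAP 8.10 applies to the trial-emergent displays, since no exception is stated, and that a listing without a stated population covers everyone in the database. If the listing of all AEs were in fact run on dosed subjects only, the gap would be more serious. The SAP should therefore settle this.

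**What to change.** In SAP 8.1 and 8.10.2:

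- Base the trial-emergent row of the overall AE summary and the trial-emergent SOC/PT table on the Enrolled Population, with its own N in a footnote. Add the matching exception to SAP 8.10.
- Within those displays, show serious trial-emergent AEs and those leading to discontinuation, so that Protocol 8.2.2 is met.
- Keep the Safety Population for all TEAE tables.
- State in one line that the listing of all AEs covers all enrolled subjects.
- Say how the all-patients wording in Protocol 8.1 and the safety-population wording in 8.1.2 are reconciled.

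No new data are needed, because SAP 6.6.2 already requires AEs to be recorded from consent. The change will not recover pre-dose SAEs that go unreported under Protocol 7.7.4. The cost is a few lines of text, a population switch for one row and one table, and two denominators in the overall AE summary, which must be labelled so that the rows are not compared as if they shared one N.

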8.10.1 Extent of Exposure and Compliance to Study Treatment

The total dose administered (mCi) of Florbetapir F 18 or Flortaucipir F 18 will be summarized using descriptive statistics. All exposure data captured on the CRF will be presented in listing.

8.10.2 Adverse Events

All AE summary tables will include only TEAEs, unless otherwise specified.

Adverse events will be summarized by SOC and PT. A subject will only be counted once per SOC and PT.

For AEs by severity grade (mild, moderate, severe), if a subject has multiple events occurring in the same SOC or same PT, then the event with the maximum intensity (i.e. severe) will be counted.

For AEs by relationship to study drug and protocol procedure will be summarized as Related vs. Not Related. If a subject has multiple events occurring in the same SOC or same PT, the event associated with the study drug will be summarized.

AEs will be summarized by descending frequency, then alphabetically by SOC and preferred term.

An overall summary of AEs will be presented and will include:

- Subjects with any Trial Emergent AEs
- Subjects with at least one TEAE
- Subjects with any severe or moderate TEAE
- Subjects with any TEAE related to Florbetapir F 18
- Subjects with any TEAE related to Flortaucipir F 18
- Subjects with any TEAE related to protocol procedure
- Subjects with any serious TEAE
- Subjects with any TEAE resulting in death
- Subjects with any TEAE leading to study discontinuation

The following summary tables will be presented by SOC and PT:

- Trial Emergent AEs
- All TEAEs
- TEAEs by PT
- TEAEs by severity
- TEAEs by relationship to Florbetapir F 18
- TEAEs by relationship to ¹⁸F-AV-1451
- TEAEs by relationship to protocol procedure
- Serious TEAEs
- TEAEs resulting in death
- TEAEs leading to study discontinuation

The following listings will be presented by subject:

- All AEs
- Serious TEAEs
- TEAEs leading to study discontinuation
- TEAEs resulting in deaths

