7. PROCEDURES AND METHODS

7.1. Assessment Periods (See Section 11.2, Trial Flow Chart)

The study will consist of the following sequence of activities:

7.1.1. Screening Visit: Visit 1

Screening may take place over several days. All screening assessments will preferably be performed within 60 days prior to the ¹⁸F-AV-1451 PET imaging session.

Screening assessments will include:

- Informed consent;
- Demographics (age, gender, education, race, ethnicity);
- Medical history, concomitant medications;

- Disease history (date/months since symptom onset, date/months since diagnosis, family history of relevant neurologic disease);
- An ECG will be performed to assess the subject’s cardiac status. If an ECG was performed within the last 12 months and is available for review, the ECG does not need to be repeated;
- Cognitive status interview, including MMSE;
- MRI of the brain, only for those subjects who do not have a prior MRI (obtained within one year of enrollment) available for submission to Avid and are able to tolerate one;
- Serum pregnancy test (women of childbearing potential);
- A physician will see the patient during the screening visit.
- Florbetapir F 18 PET scan (see section [7.1.1.1](#) for details)

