8.2.2. Safety Analyses

Adverse events including injection site reactions will be summarized in terms of number and percentage of patients experiencing an AE. The AEs will be summarized by system organ class (SOC) and preferred term using Medical Dictionary for Regulatory Activities (MedDRA) terms. Adverse events will also be presented by severity, relationship to treatment, and seriousness. All patients who experience SAEs, or who discontinue due to AEs, will be summarized.

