5.2 Changes from the Analyses Planned in the Protocol/CIP

There are no changes from the analyses planned in the Protocol/CIP at the time of preparing this SAP.

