TEAEs are defined as any AEs that occur or worsen (increase in intensity and/or frequency) after administration of Flortaucipir F 18 or Florbetapir F 18 and until 48 hours post administration.

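### The SAP limits SAE, death and AE-discontinuation displays to events within 48 hours of an injection, although the protocol promises to summarise all such patients

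*SAP*

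**What the plan says.** Protocol 8.2.2 (Safety Analyses) states: "All patients who experience SAEs, or who discontinue due to AEs, will be summarized". It attaches no treatment-emergent condition and no time window. Protocol 8.1.2 bases safety evaluation on the Safety Population, meaning anyone given at least one dose of either tracer. SAP 8.1 uses the same definition.

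SAP 8.10.2 sets the default "All AE summary tables will include only TEAEs, unless otherwise specified". Its overall summary contains "Subjects with any serious TEAE", "Subjects with any TEAE leading to study discontinuation" and a TEAE row for death. The matching SOC/PT tables and by-subject listings carry the same restriction. The exceptions are one overall row and one SOC/PT table for trial-emergent AEs, and a listing of all AEs.

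SAP 6.6.2 defines a TEAE as an AE that occurs or worsens "after administration of Flortaucipir F 18 or Florbetapir F 18 and until 48 hours post administration". A trial-emergent AE falls after consent and before florbetapir, or "between the Florbetapir F 18 injection session and Flortaucipir F 18 injection session but outside the 48 hours window".

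SAP 5.2 states: "There are no changes from the analyses planned in the Protocol/CIP at the time of preparing this SAP".

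**The concern.** The protocol promises a summary of every patient with an SAE or an AE-related discontinuation. The SAP delivers it only for events that start or worsen within 48 hours of an injection, and does not record this as a change. A subject can be in the Safety Population, and so in the denominator, with a serious or treatment-ending event correctly entered on the AE pages, and still not be counted in the matching row, table or listing.

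The study's secondary objective is to expand the flortaucipir safety database (SAP 3.2). SAEs, deaths and AE withdrawals are the results a reader of that database looks for first, and in a study of this size each one is visible. A count that omits a recorded event because of a timing filter understates what was collected.

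**Working it through.** The documents give no figure to reproduce, so the check is to follow recorded events through the SAP's categories.

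**Step 1: which events are recorded at all.** Protocol 7.7.2 keeps post-dose events outside 48 hours off the AE pages unless the investigator attributes them to the drug. It also says that trial-emergent AEs are reported outside the windows. Protocol 7.7.4 excludes an SAE before study drug unless a protocol procedure may have caused it. It keeps a related SAE after 48 hours in the eCRF as an AE. The cases below are limited to events that these rules admit, in subjects who received at least one tracer.

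**Step 2: where each one goes under SAP 6.6.2 and 8.10.2.**

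| Recorded event | SAP category | Summary tables it enters | Where it is missing |
|---|---|---|---|
| A. AE starting more than 48 h after florbetapir and before flortaucipir, attributed to the drug; subject withdraws | Trial-emergent | Trial-emergent row and SOC/PT table; the withdrawal is in disposition | AE-discontinuation row, table and listing |
| B. SAE before any dose, caused by a procedure; subject is later dosed | Trial-emergent | Trial-emergent row and SOC/PT table, with nothing to show that it was serious | SAE row, table and listing |
| C. SAE starting more than 48 h after flortaucipir, attributed to the drug | Neither: past the TEAE window, and the trial-emergent category stops at the flortaucipir session | None | SAE row, table and listing (and those for death, if fatal); it reaches only the listing of all AEs |

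The filter acts on when the AE starts or worsens, not on the date of withdrawal. An AE that starts inside a window and leads to a later withdrawal is still counted.

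**Step 3: scale, for illustration only.** Protocol 7.1.1 says: "All screening assessments will preferably be performed within 60 days prior to the ¹⁸F-AV-1451 PET imaging session". Protocol 7.1.2 asks for at least 16 hours between the scans. Assume that florbetapir is given on study, *d* days before flortaucipir. The share of the between-scan interval outside the 2-day florbetapir window is max(0, *d* − 2)/*d*:

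- *d* of 2 or less: 0%
- *d* = 7: 5/7 = 71%
- *d* = 14: 12/14 = 85.7%
- *d* = 30: 28/30 = 93.3%
- *d* = 60: 58/60 = 96.7%

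These are shares of calendar time, not of events. The documents give neither the actual gap nor an AE rate.

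**Step 4: weight of one event.** If the Safety Population were 25, the planned maximum enrolment, one omitted subject would be 1/25 = 4 percentage points. The figure is larger with fewer subjects. It is smaller if subjects given florbetapir and then screened out bring the population above 25.

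**The case against.** The strongest reply is that the gap is narrow and partly covered elsewhere. Much of that stands.

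- SAP 8.2 summarises reasons for discontinuation without a TEAE filter and lists every subject who discontinued. Trial-emergent AEs have their own row and table, and all AEs are listed. The protocol says only that these patients will be summarised, not in which table. This weakens the discontinuation half. It does not answer the SAE half, because no summary table shows seriousness for non-TEAE events.
- The protocol's own collection rules keep many out-of-window events off the AE pages, whatever the SAP does. For an unattributed AE between the scans, recording depends on which sentence of Protocol 7.7.2 governs. Only recorded events are at issue.
- The tables are labelled as TEAE tables, and the study is descriptive, so no error rate or sample size is affected.

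A reader might also draw stronger conclusions that the documents do not support:

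- *Subjects admitted on a historical amyloid scan who leave before flortaucipir are lost through the TEAE filter.* They received no study tracer, so the Safety Population excludes them in both documents. The same holds for anyone leaving before a first dose.
- *The SAE and discontinuation tables must read near zero.* In-window events are counted, including SAEs and deaths up to 48 hours after either injection.
- *After flortaucipir only about 105 minutes (75 + 30, to the end of the scan) are covered.* Because SAP 4.1 ends participation at scan completion, that limit can bear on study discontinuation only. For SAEs and deaths the window is the full 48 hours.
- *A disposition count that differs from the AE-discontinuation count shows a contradiction.* Disposition uses the Enrolled Population and AE tables the Safety Population, so some difference is legitimate.

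**Conclusion.** The mismatch holds for recorded events in dosed subjects. Protocol 8.2.2 covers all patients with SAEs or AE discontinuations, SAP 8.10.2 covers only those whose event is treatment-emergent, and SAP 5.2 wrongly reports no change. The most serious gap is a drug-attributed SAE more than 48 hours after flortaucipir, which the protocol requires to be recorded and which the SAP places in no summary table. Next is a procedure-caused SAE before dosing, tabulated without its seriousness. AE withdrawals between the scans are the mildest, because disposition partly shows them.

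The number of events affected cannot be derived from the documents and may be zero. The exposed share of between-scan time runs from 0% to about 97%, depending wholly on the assumed gap. The conclusion rests on the investigator recording the event as Protocol 7.7.2 and 7.7.4 allow, and on the subject having had at least one dose. It is worth correcting before database lock, but it does not call the imaging results into question.

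**What to change.** In SAP 8.10.2, define the overall rows, SOC/PT tables and listings for SAEs, deaths and AEs leading to discontinuation on all recorded AEs in the Safety Population. Show three groups separately:

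1. treatment-emergent;
2. trial-emergent;
3. later drug-attributed, for events more than 48 hours after flortaucipir, which at present have no category.

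The TEAE counts stay visible as now. Cross-check the AE-discontinuation count against the SAP 8.2 disposition summary, and explain any difference that comes from the Enrolled and Safety Populations. If the sponsor prefers to keep the TEAE restriction, the minimum is to declare it in SAP 5.2 as a departure from Protocol 8.2.2, although the promised summary would then still be missing.

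The cost is SAP wording and a filter change in the affected displays. No new data are needed. The SAE and discontinuation counts may become slightly less favourable.
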